8.7.2.5.4 Other Sensitivity Analysis

Not applicable.

Protocol Number: 20240175

Date: 27 March 2025 Page 33 of 47

8.7.3 Analysis of Safety Endpoints

All patients participating in the study who meet the eligibility criteria will be included in the safety analysis. All AEs will be coded using MedDRA. For safety outcomes defined in Section 8.3.2, count and proportions will be calculated, respectively.

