6.4 Statistical Inference (Estimation)

The objectives of this study are descriptive in nature and will only include estimations, no hypotheses will be tested.

Protocol Number: 20240175

Date: 27 March 2025 Page 19 of 47

7. Research Question and Objectives

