8.5 Study Sample Size

This is a descriptive study in which patient-level data on safety, OS, CCI

By the time of data cut-off, there will be approximately 100 sotorasib treated patients in BOAO Pilot Zone assuming all sites are eligible, and about 15 patients in Hong Kong SAR, will be eligible for enrollment.

The estimation precision of parameters is provided based on the preliminary sample count of all patients treated with sotorasib in BOAO Pilot Zone and Hong Kong SAR. The formular, based on the normal approximation to the binomial distribution, for calculating the precision (ie, margin of error, which is represented by one half the desired width of the confidence interval) given a proportion and sample size is as the following:

$$e = \sqrt{\frac{px (1-p)x (Z_{1-\frac{\alpha}{2}})^{2}}{n}}$$

Where P is the expected proportion of interest, n is the sample size, and $Z_{1-\frac{\alpha}{2}}$ is the standard normal Z value corresponding to a cumulative probability of $(1-\frac{\alpha}{2})$ (eg, if α = 0.05 then Z=1.96). The following table (Table 1) provides the estimated precision based on the sample size of patients who received sotorasib (N = 115, tentatively) and various proportions of interest.

Protocol Number: 20240175

Date: 27 March 2025 Page 27 of 47

Table 1. Precision based on the sample size by various proportions

Proportion (1- proportion)	Sample size of patients	The margin of error (absolute precision)
50% (50%)	115	9.14%
40% (60%)	115	8.95%
30% (70%)	115	8.38%
20% (80%)	115	7.31%
10% (90%)	115	5.48%

As the proportion of interest (p) (eg, proportion of treatment-related AEs of grade 3 or worse) in this study is not known in advance, we consider the proportion to be 50% (maximum uncertainty). Such an assumption yields the most conservative, ie, the largest level of margin of error (indicating the lowest level of precision), with is $\pm 9.14\%$.

The sample size of patients treated with sotorasib will be confirmed during data cleaning and data analysis phase.

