8.7.2 Planned Method of Analysis

8.7.2.1 General Considerations

All data analyses will be performed using appropriate software such as SAS statistics software version 9.3 or higher (SAS Institute Inc., Cary, NC). An analysis plan with a detailed description of analyses to be performed will be developed.

All analysis will be conducted separately for patients in BOAO Pilot Zone and Hong Kong SAR CDARS.

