8.7.2.4 Analysis of the Primary, Secondary, and Exploratory Endpoint(s)

Frequencies will be presented for categorical demographic (eg, sex, smoking status), clinical (eg, prior treatments, tumor mutations), and pathological (eg, stage, histology) variables. Descriptive statistics (mean, median, standard deviation, and range) will be presented for continuous variables.

The proportion of AEs will be summarized by count and proportions, specifically the proportion of patients experiencing AEs relative to the total number of patients.

Median OS and PFS and the corresponding 95% confidence intervals (CIs) will be calculated using Kaplan-Meier estimates. The estimated survival probabilities, along with corresponding 95% CIs using Kaplan-Meier method will be presented for patients at 6 and 12 months.

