10.2 Safety Collection, Recording and Submission to Amgen Requirements

This study is analyzing secondary data from electronic health record databases. The safety outcomes that are listed in Section 8.3.2 will be documented and analyzed in this study. These will be reported in aggregate in the final study report as counts and proportions. See Section 8.3.2 for safety outcomes and definitions. Reportable events suspected to be related to any Amgen medicinal product, combination product or device should be spontaneously reported to Amgen within 1 business day of investigator/vendor awareness. A list of all Amgen medicinal products can be found in the following link: https://www.ext.amgen.com/amgen-worldwide

To spontaneously report a reportable event to Amgen, refer to the following link to locate your Local Amgen contact information by country:

https://wwwext.amgen.com/contact-us/product-inquiries

Additional details on what to collect and report to Amgen for the reportable event can be found in the following link: https://www.ext.amgen.com/products/global-patient-safety/adverse-event-reporting. Reportable events suspected to be related to any non–Amgen medicinal product should be reported to the local authority in line with the local country requirements.

11. Administrative and Legal Obligations

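### The study is sized on the confidence-interval width of an AE proportion in 115 pooled patients, yet its primary AE analysis states no interval and is run by region

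*Protocol*

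**What the plan says.** Protocol Section 6.4 sets the framework: the objectives "will only include estimations, no hypotheses will be tested". Section 8.5 then justifies the sample by precision alone. It defines the margin of error as half the width of a confidence interval and gives a formula "based on the normal approximation to the binomial distribution". Table 1 applies it at 115 patients to proportions from 50% down to 10%, and ±9.14% is called the largest margin. The example proportion is treatment-related AEs of grade 3 or worse.

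The analysis of the primary endpoint is described as follows:

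- Section 8.7.2.4: "The proportion of AEs will be summarized by count and proportions".
- Section 8.7.3: "For safety outcomes defined in Section 8.3.2, count and proportions will be calculated, respectively".
- Section 10.2, on the final report: "These will be reported in aggregate in the final study report as counts and proportions".

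The data analysis paragraph of the abstract (Section 4) has the same content. None of these places attaches an interval to an AE proportion. In contrast, Section 8.7.2.4 says of the time-to-event endpoints: "Median OS and PFS and the corresponding 95% confidence intervals (CIs) will be calculated using Kaplan-Meier estimates". It also gives 95% intervals for survival at 6 and 12 months.

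Section 8.7.2.1 adds: "All analysis will be conducted separately for patients in BOAO Pilot Zone and Hong Kong SAR CDARS". Section 8.3.2 limits Hong Kong to the AEs of interest (hepatotoxicity, interstitial lung disease/pneumonitis, renal toxicity). Expected numbers are about 100 patients in BOAO and about 15 in Hong Kong.

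**The concern.** In an estimation-only study, the result is the estimate together with its uncertainty. Here the width of the interval around an AE proportion is the only reason given for regarding the sample as sufficient, yet the text describing the primary output does not ask for that interval. The secondary endpoint gets one; the primary does not.

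The precision that is quoted also belongs to no analysis the protocol plans. It is for 115 patients together, while the analyses are separate. For the example used in 8.5, grade 3 or worse treatment-related AEs, Hong Kong does not contribute at all, so the denominator is about 100 at most.

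Two things are at stake. A line such as 0 of 15 for pneumonitis could be read as reassuring when it leaves a high true rate possible. And if the protocol is silent, the only formula it gives for a simple proportion could be carried over from planning into reporting, where it behaves badly for small samples and rare events.

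**Working it through.** **Inputs.** From Section 8.5: N = 115 pooled, about 100 BOAO, about 15 Hong Kong, α = 0.05 with Z = 1.96, and the proportions in Table 1. From Section 8.7.2.1: analysis by region. The protocol gives no expected rate for the AEs of interest, so any true rate used for coverage below is an assumption.

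**Step 1: the plan's own figures.** The half-width is e = 1.96 × √(p(1−p)/n). At n = 115:

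- p = 50%: 1.96 × √(0.25/115) = 9.14%
- p = 40%: 8.95%
- p = 30%: 8.38%
- p = 20%: 7.31%
- p = 10%: 5.48%

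All five rows of Table 1 reproduce.

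**Step 2: the same formula at the sizes actually analysed, p = 50%.**

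- n = 100: 1.96 × √(0.25/100) = ±9.80%
- n = 15: 1.96 × √(0.25/15) = ±25.30%

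Both exceed the stated maximum of ±9.14%. The BOAO difference is small; the Hong Kong margin is nearly three times as wide (25.30/9.14 = 2.8).

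**Step 3: what low counts can tell the reader.** The exact (Clopper-Pearson) limits come from beta quantiles. With zero events the upper limit is 1 − 0.025^(1/n): 1 − 0.025^(1/15) = 21.8% and 1 − 0.025^(1/100) = 3.6%. The normal-approximation (Wald) interval is p̂ ± 1.96 × √(p̂(1−p̂)/n).

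| Events | Wald 95% | Exact 95% |
|---|---|---|
| 0/15 | 0 to 0% | 0 to 21.80% |
| 1/15 | −5.96 to 19.29% | 0.17 to 31.95% |
| 2/15 | −3.87 to 30.54% | 1.66 to 40.46% |
| 0/100 | 0 to 0% | 0 to 3.62% |
| 1/100 | −0.95 to 2.95% | 0.03 to 5.45% |
| 5/100 | 0.73 to 9.27% | 1.64 to 11.28% |

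**Step 4: coverage of a nominal 95% interval.** Coverage is the sum of binomial probabilities over all counts whose interval contains the true rate. At an assumed true rate of 5%:

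- n = 15: Wald 53.6%, Clopper-Pearson 99.5%. The loss is almost all from zero-event samples, which have probability 0.95^15 = 46.3% and give a zero-width Wald interval.
- n = 100: Wald 87.7%, Clopper-Pearson 98.3%.

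At n = 100 and 115, for the rates tried from 10% to 50%, Wald coverage is 93.2% to 95.2%. The approximation is therefore adequate over the range Table 1 displays at those sizes. At n = 15 it is not: coverage is 79.2% at an assumed 10% and still only 88.2% at 50%.

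**The case against.** The strongest reply is that Section 8.7.2.1 announces a separate analysis plan, which is not available here. Whether AE tables carry an interval, and by which method, is commonly settled there, and reporting counts and proportions does not exclude intervals. This stands as far as the choice of method goes: leaving exact versus Wilson to the analysis plan would be no fault. It does not remove the mismatch inside the protocol, which itself names intervals for survival, names only counts and proportions for AEs in several places, and rests its size on the AE interval width.

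A reader might infer that the protocol intends to report normal-approximation intervals for AEs, making the drug look safer than the data allow. The document does not support that. The formula appears only in 8.5, for planning, and no section adopts it for reporting. Nor is it the only interval method in the protocol, since Kaplan-Meier intervals are also specified; it is the only one for a simple proportion.

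A reader might also infer that Table 1 is wrong or unsuitable for its purpose. It is arithmetically correct. The cited trials' overall benchmarks (69.8% for any treatment-related AE; 19.8% for grade 3 and 33% for grade 3 or worse) lie where the approximation works at about 100 patients. The 8% and 5% quoted for ALT and AST increase are single-term, treatment-related, grade 3 or worse rates. They do not show that hepatotoxicity, defined through a grouped MedDRA query, will be rare.

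Finally, anyone given 0 of 15 can compute an exact interval. That is true, and no estimate is biased. But a study whose declared output is estimation should not leave that calculation to its readers.

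**Conclusion.** The point holds as an inconsistency within the protocol. Followed as written, 8.7.2.4, 8.7.3 and 10.2 produce primary results without the measure of precision on which 8.5 rests. The precision quoted there is for a pooled sample that the separate regional analyses do not use: ±9.14% stated, against ±9.80% for BOAO and ±25.30% for Hong Kong at a proportion of 50%. In exact terms, no events would remain compatible with true rates up to 21.8% in 15 patients and 3.6% in 100.

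The warning about the normal approximation is conditional: it matters only if the planning formula is reused for reporting. The coverage figures rest on assumed true rates, and all regional figures rest on the protocol's approximate counts of 100 and 15. It does not follow that any planned interval is wrong, because none is stated for AEs.

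**What to change.** In 8.7.2.4 and 8.7.3, state that each primary AE proportion is reported by region with its denominator and a two-sided 95% Clopper-Pearson interval; align the sentence in 10.2 and the abstract. Clopper-Pearson is the safer choice for the Hong Kong group: its coverage was at least 95% at every rate tried, while Wilson fell to 86.0% at n = 15 with an assumed true rate of 1%.

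In 8.5, replace the pooled margins with exact limits at n of about 100 and about 15. Add rows below 10%, labelled as assumed rates, and give the upper limit for zero events (3.6% and 21.8%). Remove the description of ±9.14% as the largest margin, and note that grade 3 or worse treatment-related AEs are estimated from BOAO patients only.

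The cost is a few sentences and a recalculated table, with no new data. The one downside is that the stated precision becomes less favourable, markedly so for Hong Kong.

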8.8 Quality Control

At the study level, all aspects of the study from protocol development to the reporting of the results are conducted following Standard Operating Procedures (SOPs) developed by Amgen and/or the vendor.

The investigator, co-investigator(s) and all site staff involved in the study will be trained on the conduct of the study at the time of site initiation. To ensure the integrity of the data, to examine compliance with the protocol and adherence to the data extraction procedures, and to verify that records and documents are being properly maintained for the duration of the study, sites will be monitored both onsite and remotely by the vendor.

Once all data has been entered and all outstanding monitoring issues have been addressed, all sites will be closed out remotely. Monitor contact details for each participating site will be maintained in the Investigator Site File.

All functions, processes, and specifications for data extraction, cleaning and validation will be described in a data curation plan. This plan will be completed prior to the start of data abstraction.

In case data are missing, out of range, illogical or potentially erroneous, the eCRF, that includes automated edit checks, will give immediate feedback and ask for correction.

Thus, high data quality standards will be obtained, and processes and procedures to ensure that the data are as clean and as accurate as possible will be put into practice. A series of programmed data quality checks that automatically detect outages will enhance data quality.

Written programming will be reviewed independently. The secure storage of data, study programs, log files, output files and back up will be ensured as required by regulatory guidelines.

Protocol Number: 20240175

Date: 27 March 2025 Page 34 of 47

8.9 Limitations of the Research Methods

8.9.1.1 Measurement Errors

As no verified death information is linked (eg, death registry) in BOAO Pilot Zone, the reported death is used. Because of this, it is likely the survival is underestimated. Sensitivity analysis excluding those lost to follow up will be performed.

8.9.1.2 Confounding

Not applicable.

8.9.2 External Validity of Study Design

All Chinese adult patients with *KRAS p.G12C*-mutated locally advanced or metastatic NSCLC who were treated with sotorasib in BOAO Pilot Zone and Hong Kong SAR will be eligible for enrollment. With limited exclusion criteria, this study population well represents Chinese *KRAS p.G12C*-mutated locally advanced or metastatic patients with NSCLC treated in real-world. Patients need to be able to travel to get treatment at BOAO Pilot Zone, indicating better health status and social economic status of the study population.

8.9.3 Analysis Limitations

CCI
We will perform a sensitivity analysis in which patients who
switch to other commercially available drugs or clinical trial medications will be censored
for sotorasib treatment.
Estimates of OS are likely to be immature in this study due to the potentially short
observation period for some patients. Patients without evidence of death by the data
cut-off will be censored at their last confirmed activity date, potentially underestimating
the true time at risk. A sensitivity analysis will follow these patients to the end of the
study instead of censoring them at their last confirmed activity date.
CCI

Protocol Number: 20240175

Date: 27 March 2025 Page 35 of 47

No further analysis limitations are expected.

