8.2.1 Study Period

The study eligibility period extends from the patients' index date (ie, the initiation of sotorasib) to the end of study period, defined as the earliest occurrence of patient's last activity date in the data source, data cut-off date or death.

The first available sotorasib use in BOAO Pilot Zone is around August 2021 through a pre-registration program. Specifically, sotorasib was included in the following hospitals'

Protocol Number: 20240175

Date: 27 March 2025 **Page 20 of 47**

drug lists and available for prescription: Ruijin Hainan Hospital in July 2022; BOAO Super Hospital in August 2021; BOAO Hengda Hospital in November 2021; and BOAO future Hospital in January 2022. The data cut-off will be the EC submission date (~ Q2 2025).

Sotorasib was approved in Hong Kong on April 29, 2022. The eligible treatment should occur after April 29, 2022. The data cut-off will be the date of data extraction (~ Q3 2025).

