8.2.6 Study Follow-up

As the Hong Kong SAR CDARS database is a closed-loop database with linkage to the regional deaths registry, patients without evidence of death in the CDARS database by the data cut-off date were considered alive, and their last activity date will be the same as the cut-off date.

For the objective of OS, follow-up per patient will continue through earliest date of last clinical activity in the data source, data cut-off in the data source, or death.

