8.3.2 Outcome Assessment

Safety Outcomes

In BOAO Pilot Zone, the AEs recorded in the electronic health record database throughout the study period will be documented and analyzed. Detailed information in medical records including vital signs, concomitant treatments, results of routine laboratory testing, ECG, and radiology will be reviewed to verify these AEs. Severity grade of AEs will be further verified by investigators according to the Common Terminology Criteria for Adverse Events (CTCAE), version 5.0 (CTCAE v5.0).

The patient incidence of AE after sotorasib initiation, including:

- TEAE
- Adverse event of interest, inclusive of hepatotoxicity, interstitial lung disease/pneumonitis, and renal toxicity
- Treatment-related AEs
- Treatment-related AEs of grade 3 or worse
- Serious treatment-related AEs
- Treatment-related AEs leading to treatment discontinuation
- Treatment-related AEs leading to dose reduction
- Treatment-related AEs leading to death

[figure not shown]
In Hong Kong SAR CDARS database, only adverse event of interest, inclusive of hepatotoxicity, interstitial lung disease/pneumonitis, and renal toxicity will be documented and analyzed. Each event of interest is a grouping of individual preferred terms determined using the following standardized MedDRA queries (SMQs): drug-related hepatic disorders – comprehensive search (SMQ narrow) for hepatotoxicity; interstitial lung disease (SMQ narrow) for ILD/pneumonitis; and acute renal failure (SMQ narrow) for renal toxicity. Medical records including diagnosis, vital signs, concomitant treatments, results of routine laboratory testing, ECG, and radiology will be reviewed to identify and verify AE. Detailed testing and exams to review will be further clarified in the statistical analysis plan and eCRF.

Protocol Number: 20240175

Date: 27 March 2025 Page 23 of 47

OS

• OS: The time from the index date to death from any cause. Patients without evidence of death at data cutoff will be right-censored at their last activity date.

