8.7.2.5.3 Sensitivity Analysis for Residual Confounding and Bias

In the absence of verified death information in BOAO Pilot Zone, such as data from death registries, the reported deaths are utilized for analysis. This may introduce a potential for underestimating survival rates. A sensitivity analysis will be conducted by excluding individuals who were lost to follow-up defined as those whose last activity is earlier than the data cutoff. The characteristics of patients with censoring will be outlined alongside those of patients without censoring, providing insights into their respective profiles.

We will also conduct a sensitivity analysis wherein patients with other actionable mutations (eg, ALK, EGFR) who have received treatment with targeted therapies other than sotorasib will be excluded, as the prognosis among such patient populations could be meaningfully different compared to patients not receiving these targeted therapies.

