8.9.4 Limitations Due to Missing Data and/or Incomplete Data

A limitation of retrospective chart review studies is that only data documented in patient medical records can be transmitted in the eCRF.

We expect that most patients with NSCLC remain at the BOAO Pilot Zone, or same site in Hong Kong SAR for the entire treatment of the disease. To meet the objectives of this study, data will be abstracted which in general are documented in the patient medical records in routine oncology care except for AE grade. Adverse events grade and relationship to sotorasib may not be available for some patients or unable to be confirmed based on the available information. Adverse events grades and relationship to sotorasib will be extracted to the extent possible. Additionally, information on deaths may be incomplete, as the analysis will only use reported deaths. Missingness and incomplete data on the covariates, and potentially others not listed here, may limit the ability to assess certain subgroup of interest. The level of missingness will be described and no attempts at imputation will be made in this study.

Since sotorasib is not widely available in mainland China, the early adopters included in this study may not be fully representative of the broader population that will eventually receive this treatment. For example, as patients are required to travel to BOAO Pilot Zone for therapy, they may generally be healthier than the average patient. Despite this limitation, this study will still provide valuable insights into the safety and effectiveness profile of sotorasib in a real-world context.

During the data abstraction period, manual queries or source data verification will be done. Additionally, missing information in mandatory variables or inconsistent data on these variables in the eCRF will be flagged directly in the eCRF so that it can be added or corrected immediately while entering the data. Furthermore, the monitor will conduct calls with the sites and/or send e-mails to establish progress, address any challenges, and refresh investigators on study responsibilities. In addition to a planned proactive outreach, the data curation will continue to manage investigator-initiated study-related enquiries as needed.

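### The sensitivity analysis that carries patients without a reported death to the end of the study can act only in BOAO, where it is an upper bound on survival and not the correction that Section 8.9.3 presents

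*Protocol*

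**What the plan says.** The main OS rule is in Section 8.3.2: "Patients without evidence of death at data cutoff will be right-censored at their last activity date". Section 8.9.3 calls this a possible understatement of time at risk and answers it with the planned analysis: "A sensitivity analysis will follow these patients to the end of the" "study instead of censoring them at their last confirmed activity date". The analysis is not limited to one region.

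The two regions differ in how they learn of deaths. For Hong Kong, which is linked to the death registry, Section 8.2.6 says that "patients without evidence of death in the CDARS database by the data cut-off date were considered alive" and sets their last activity date to the cut-off. For BOAO, Section 8.7.2.5.3 says: "In the absence of verified death information in BOAO Pilot Zone, such as data from death registries, the reported deaths are utilized for analysis". Section 8.9.4 adds that "information on deaths may be incomplete, as the analysis will only use reported deaths". On the consequence of having reported deaths only, Section 8.9.1.1 states: "Because of this, it is likely the survival is underestimated". Section 8.7.2.5.3 gives the same direction and plans a second sensitivity analysis that drops patients whose last activity falls before the cut-off.

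Section 8.7.2.1 has the two regions analysed separately.

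**The concern.** Carrying a patient forward as alive is sound where no recorded death means no death. That holds in Hong Kong, where the rule is redundant. With the regions analysed separately, the rule can change a result only in BOAO, where the protocol itself says that the premise is not secure.

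The protocol offers the result as a repair of understated time at risk and says elsewhere that missing death reports make survival look too short. A reader who follows both statements will take the upward shift as movement towards the truth. OS is the only secondary objective, and no planned analysis gives a dependable lower limit for BOAO.

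**Working it through.** **Plan figures.** The protocol states no figure for OS precision or for this bias. Its only design figure, the 9.14% margin of error in Table 1, reproduces (1.96 × √(0.25/115) = 9.14%) but has no bearing here.

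**Direction.** Let F(t) be the probability of death by t, and F₁(t) the probability of a reported death by t, so F₁(t) ≤ F(t). If every patient without a reported death stays at risk to a cut-off unrelated to survival, Kaplan-Meier estimates 1 − F₁(t). This is at least 1 − F(t), whatever the reason for loss, with equality only if every death is reported. Within one data set, later censoring enlarges the risk sets and adds no deaths, so the carried curve cannot fall below the main one. In 2,000 simulated data sets of 100 patients it never did.

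**Inputs from the protocol.** Median OS is 10.6 months (phase III figure, Sections 4 and 6.2). BOAO use starts in August 2021 with cut-off about Q2 2025 (Section 8.2.1), so about 45 months. Visits are monthly, then every 3 months (Section 8.4).

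**Assumptions.** Survival is exponential, entry is uniform over 45 months, and living patients are observed to the cut-off unless lost. The loss rates are mine. The hazard is λ = ln 2/10.6 = 0.0654 per month, and true 12-month OS is exp(−12λ) = 45.6%.

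**Scenario A: a share q of deaths is unreported, with last contact 0–3 months before death.**
- Carried curve: 1 − (1 − q)(1 − e^(−λt)). Its median is −ln[1 − 0.5/(1 − q)]/λ.
- q = 20%: −ln(0.375)/0.0654 = 15.0 months. 12-month OS is 1 − 0.8 × 0.544 = 56.5%.
- q = 40%: −ln(0.1667)/0.0654 = 27.4 months. 12-month OS is 1 − 0.6 × 0.544 = 67.4%.
- Main curve: if last contact were at death itself, the hazard would be (1 − q)λ and the median 10.6/(1 − q) = 13.25 or 17.7. With the 0–3 month gap, simulation gives 13.0 and 17.0.

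**Scenario B: non-informative loss, with later deaths unreported.** The loss hazard is μ = −ln(1 − q)/12, where q is the share lost by 12 months.
- The main curve is unbiased: 10.6.
- The carried median is −ln[1 − 0.5(λ + μ)/λ]/(λ + μ).
- q = 20%: μ = 0.0186, median 12.2. q = 40%: μ = 0.0426, median 16.2.

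| Median OS, months (true 10.6) | Main | Carried to cut-off | Lost patients excluded | Lost patients counted as deaths at last activity |
|---|---|---|---|---|
| A, 20% unreported | 13.0 | 15.0 | 11.6 | 10.4 |
| A, 40% unreported | 17.0 | 27.4 | 13.2 | 10.2 |
| B, 20% lost by 12 months | 10.6 | 12.2 | 8.9 | 8.3 |
| B, 40% lost by 12 months | 10.6 | 16.2 | 7.4 | 6.4 |

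The A rows are simulated. In the B rows the exclusion column is simulated and the rest is closed form; the last column there is ln 2/(λ + μ). Simulated values vary by about 0.1 between runs.

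**The exclusion analysis as a bound.** It lies above the truth in A and below it in B. If living BOAO patients were last seen 0–3 months before the cut-off, as the visit schedule suggests, the definition removes nearly every survivor. The median is then about 6.9 months at either reporting level. It bounds nothing dependably.

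**The case against.** Five points on the other side deserve an answer.

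- **A downward analysis is planned.** This stands. The exclusion analysis in Section 8.7.2.5.3 lowers OS relative to the main estimate, so a reader who infers that every planned analysis leans the same way is mistaken. What is missing is a valid lower bound.
- **The main estimate need not be biased.** This also stands. One might infer that the main BOAO estimate is known to be too high. That requires loss linked to death; under non-informative loss it is unbiased. Section 6.3 describes active follow-up inside and outside BOAO, which would reduce loss, though Section 8.7.2.2 ties it to the treatment period.
- **If every death were reported, the extension would be right.** True. With early-censored survivors and full death capture, the simulated main median falls slightly (10.5 to 9.8), and carrying forward restores about 10.6. That is the Hong Kong situation; the protocol does not claim it for BOAO.
- **Section 8.2.1 might make the analysis empty.** It runs eligibility "to the end of study period, defined as the earliest occurrence of" last activity, cut-off or death, so one might infer that the extension changes nothing. Section 8.9.3 contrasts the end of the study with last activity, which rules that reading out. Naming the cut-off date would simply be clearer.
- **This is not immortal time in the usual sense.** Agreed. It is time after last contact in which a death cannot be recorded.

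**Conclusion.** The point holds in this form: in BOAO, the only place where the analysis can act, it gives an upper bound on OS, and the protocol presents it as a correction. The direction needs no assumption about why patients are lost, only that some deaths go unreported, a possibility that Section 8.9.4 concedes. If loss is linked to death, the main estimate is already optimistic and this one is more so.

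The size cannot be fixed from the protocol. Under the stated assumptions the carried median exceeds the true 10.6 months by about 1.6 to 4.4 months with 20% loss or under-reporting, and by about 5.6 to 16.8 months with 40%.

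The direction stated in Sections 8.7.2.5.3 and 8.9.1.1 is also wrong for the reason given there. An unrecorded death turns an event into a censored patient. That overstates survival when loss is linked to death and is neutral at best when it is not. The slight understatement noted above comes from censoring survivors early when all deaths are captured, which is a different mechanism.

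This is one sensitivity analysis of a secondary endpoint in a descriptive study. It should be corrected, but it does not touch the primary safety objective.

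**What to change.** 1. In Section 8.9.3, state that for BOAO the extension runs to the data cut-off date and is an upper bound (best case) only, not a correction of the main estimate.
2. Report it always beside a lower bound that counts BOAO patients last seen before the cut-off, without vital status confirmed at or after it, as deaths at their last activity date.
3. In Sections 8.7.2.5.3 and 8.9.1.1, correct the direction: incomplete death capture overestimates survival.

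The cost is wording and one more Kaplan-Meier run. Sections 8.7.2.2 and 8.9.4 rule out imputation, so the pair should be described as bounding assumptions.

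The downside is a wider displayed range. The lower bound also counts living patients whose status is unconfirmed. If no survivor seen 0–3 months before the cut-off were confirmed alive, its median in scenario A would fall to about 7 months. Confirming vital status at the cut-off, where that is possible, is what narrows the range.
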